10.6. Other actions taken

- Specific therapy/medication;
- Concomitant procedure;
- Supplementary oxygen alone;
- FiO₂ increase;
- Manual Positive Pressure Ventilation;
- Endotracheal intubation and invasive ventilation;
- Administration of adrenaline, crystalloids or colloids;
- Not applicable.

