Sample size calculation	
No primary efficacy endpoint was defined in this study since the main objective is to describe the overall safety and efficacy profile of administering poractant alfa with two different procedures: LISA technique or conventional administration with endotracheal tube and brief invasive ventilation. A total number of one hundred-fifty (150) neonates is deemed appropriate for the study aim. Neonates will be randomized with a ratio 2:1 to the LISA technique arm (i.e. 100 neonates) and to the conventional technique (i.e. 50 neonates).

Statistical methods	
Safety variables
 
 Number and percent of neonates reporting AEs started during procedure for surfactant administration as well as AEs started during the procedure and judged related to the procedure will be summarized by treatment group. 
For LISA group, any AE assessed as related to CHF 6440 medical device will be considered procedure-related.
 
These events will be also summarized by treatment group based on action required, if any (i.e. supplementary oxygen or transient increase in FiO₂, manual positive pressure ventilation, endotracheal intubation, administration of crystalloids, cardiac massage or administration of adrenaline). The duration of endotracheal intubation (invasive ventilation) and manual positive pressure ventilation will be summarized as well.
 
A subgroup analysis of surfactant- and procedure- related AEs will be performed based on the use of sedation and/or analgesia (Yes/No).
 
 Incidence of all the AEs (including neonatal complications of prematurity), related AEs (ADRs), serious AEs (SAEs) and AEs leading to death will be summarized by treatment group both in terms of frequency of neonates with at least one AE and in terms of frequency of AEs (number of events). All the aforementioned

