9. SAFETY ASSESSMENTS

The following variables will be used to describe the safety of the two procedures:

During procedure for surfactant administration

- Number and percentage of neonates with AEs starting during overall procedure for surfactant administration;
- Number and percentage of neonates with AEs starting during overall procedure for surfactant administration judged related to the procedure;
- Number of AEs occurring during overall procedure for surfactant administration requiring either oxygen alone or an increase in FiO₂ without the need for escalation of invasive or non-invasive ventilator support;
- Number of AEs starting during overall procedure for surfactant administration requiring administration of manual (bag and mask) pressure positive ventilation and related duration of ventilation (non- invasive ventilation);
- Number of AEs starting during overall procedures for surfactant administration requiring endotracheal intubation and related duration of intubation (invasive ventilation);
- Number of AEs starting during overall procedures for surfactant administration requiring circulatory support including administration of crystalloids;
- Number of AEs starting during overall procedures for surfactant administration requiring cardiopulmonary resuscitation including administration of cardiac massage or adrenaline.

After first administration

- Number and percentage of neonates with failed 1st attempt to insert the CHF6440/ETT;
- Number of attempts to the first successful insertion;
- Number of device misallocation (esophageal insertion);
- Number of maneuvers discontinued due to neonate's severe destabilization;
- Duration of the whole procedure (starting from the insertion of laryngoscope up to the removal of the catheter or ETT);
- Duration of surfactant administration (min);
- Heart rate (HR) and respiratory rate (RR) (0, 5, 15 and 30 min, 1 hour, 6 and 12 hours after administration);
- Systolic, diastolic, and mean blood pressure (SBP/DBP/ MBP) (15 and 30 min, 1 hour, 6 and 12 hours after administration);
- Premature Infant Pain Profile (PIPP) score [26] (end of surfactant administration).

During the study

- AEs, including incidence of major neonatal complications of prematurity (listed in [APPENDIX III](#)) and adverse drug reactions (ADRs);
- Blood pressure (SBP, DBP, MBP) at 24, 48, 72, 120 hours post-administration;

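### The adverse-event action list in Section 10.6 pools adrenaline with fluids and names no cardiac massage, so on its own it cannot separate circulatory support from CPR as Section 9 counts them

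*Protocol*

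**What the plan says.** Section 9 of the protocol, under the heading for the period of the procedure, defines five variables by what an AE required. The outline repeats them. The last two are "Number of AEs starting during overall procedures for surfactant administration requiring circulatory support including administration of crystalloids" and "Number of AEs starting during overall procedures for surfactant administration requiring cardiopulmonary resuscitation including administration of cardiac massage or adrenaline".

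The planned analysis follows the same division. The outline (Statistical methods, safety variables) summarises these events by the action required, and its list ends with "administration of crystalloids, cardiac massage or administration of adrenaline". Section 12.3.5 gives a similar list in which crystalloids, cardiopulmonary resuscitation and adrenaline are separate items.

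Section 10.6 is the only place where the protocol lists actions taken for an AE, other than action on the study drug. One of its options is "Administration of adrenaline, crystalloids or colloids". None names cardiac massage or CPR. Two options are generic: "Specific therapy/medication" and "Concomitant procedure".

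**The concern.** The recorded categories do not line up with the variables they appear meant to feed. An AE treated with a crystalloid bolus and an AE treated with adrenaline get the same code, although Section 9 puts the first under circulatory support and the second under CPR. An AE treated with cardiac massage but no adrenaline has no code of its own.

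The main objective (Section 2.1) is the safety profile of the procedure. Section 10.8 asks for particular attention to bradycardia and to treated hypotension during it, and Section 6.2.3.5 provides for resuscitation during administration. The affected events are therefore ones that the protocol foresees. At stake is whether the report can say, by arm, how many procedural AEs led to resuscitation and how many only to fluids, without someone assigning cases after the event in an open-label trial.

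**Working it through.** No stated figure is involved, so there is nothing to recompute. The check is to map each action-based variable in Section 9 to the options in Section 10.6.

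| Section 9 variable (AEs starting during the procedure) | Option(s) in Section 10.6 | Match |
|---|---|---|
| Oxygen alone or higher FiO2, no escalation of support | Oxygen alone; FiO2 increase | Yes |
| Bag-and-mask ventilation | Manual positive pressure ventilation | Yes |
| Endotracheal intubation | Intubation with invasive ventilation | Yes |
| Circulatory support, including crystalloids | Pooled adrenaline/crystalloids/colloids | Ambiguous |
| CPR, including cardiac massage or adrenaline | Pooled option for adrenaline; generic procedure option for massage | Ambiguous |

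Three of five variables have matching options, and 5 − 3 = 2 do not. The close match in the first three rows suggests that Section 10.6 was written to supply these variables, though the protocol does not say so.

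Next, whether other records could close the gap:

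- **Medications.** Section 5 requires medications to be recorded in the eCRF, apart from a short list of prophylactic products that includes neither adrenaline nor fluids. Section 6.2.3.2 asks for date, time, dose and route of medications around the procedure.
- **Procedures.** Section 11 has concomitant procedures coded in MedDRA, so massage can be entered there.
- **SAE forms.** Section 6.2.3.5 ties resuscitation during administration to a life-threatening event. Section 10.1 makes such an event serious, and Section 10.8 then requires a separate SAE form.

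Reconstruction is therefore possible. What is missing is a stated link between a medication or procedure record and an individual AE. Section 9 counts AEs, not neonates. Several AEs, such as bradycardia, desaturation and hypotension, may start within one procedure, and matching on time alone need not show which of them a given treatment was for.

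For scale, Section 12.1 plans 100 LISA and 50 control neonates. If the events were expressed per neonate, one case would be 1/100 = 1 percentage point in the LISA arm and 1/50 = 2 percentage points in the control arm. The protocol gives no expected rate of fluid treatment or CPR, so the number of AEs that would be ambiguous cannot be estimated from it.

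**The case against.** A reader might infer that the two variables cannot be derived at all, or that resuscitation events would vanish from the data. The documents do not support that. Adrenaline and fluids should appear among the medications, massage can be entered as a procedure, and a resuscitated neonate should have an SAE report. Under Section 6.2.3.5 resuscitation starts with positive pressure ventilation, so such an AE would normally also carry that action and be flagged. The window is short as well: Section 10.8 ends the procedure at removal of the catheter, or of the tube within one hour of instillation. Case review of a few events is feasible. All of this stands, and it limits the point to what the action field can do alone.

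It can also be said that Section 10.6 does not declare its list closed or single-choice, whereas Section 10.7 on outcome does require a choice among listed values. The eCRF is not shown and may hold finer fields. That is fair. If so, Section 10.6 should still be brought into line with it.

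The word *including* in both definitions means that they are illustrative and may overlap. This does not remove the ambiguity: an AE treated only with crystalloids is not thereby a CPR event, yet it shares a code with one treated with adrenaline.

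Lastly, derivation rules may be left to the SAP. A SAP could direct the analyst to other records, but it cannot split a category that was merged when the data were collected. The conflict here is between two stated parts of the protocol, so it is more than missing detail.

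**Conclusion.** The point holds in limited form. Section 10.6 does not match Section 9 or the planned summaries by action, and the action field as listed cannot separate two of the five action-based procedural safety variables. Both would have to be rebuilt from medication, procedure and SAE records, without a stated AE-level link.

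The conclusion assumes that the eCRF field follows Section 10.6 as printed. The consequence is confined to descriptive safety counts, since Section 12.3.5 only summarises these events by arm with no test or decision rule. Sample size and error rates are unaffected. It would go too far to say that miscoding would decide the trial's safety conclusion: the protocol gives no rates from which to judge that. The change is still worth making, because it is nearly free and concerns serious events under the trial's main objective.

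**What to change.** In Section 10.6 and the matching eCRF field:

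1. Replace the pooled option with two: crystalloids/colloids or other circulatory support; and adrenaline.
2. Add an option for cardiac massage/CPR.
3. Allow more than one action per AE.
4. State that the first option feeds the circulatory-support variable in Section 9, and that the adrenaline and cardiac massage/CPR options feed the CPR variable. Use the same terms in the outline and in Section 12.3.5.

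If the field cannot be changed, state instead that both variables are derived from medication and procedure records linked to the AE, and add that link. For AEs already entered, re-code from the medication, procedure and SAE records.

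The cost is a small edit to one protocol list and one eCRF field, plus a short round of data queries for any AEs already recorded. It needs no new assessment and changes no clinical rule.

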10.7. Outcome

Each Adverse Event outcome must be described by choosing among:

- Recovered/resolved;
- Recovering/resolving;
- Not recovered/not resolved;
- Recovered with sequelae/resolved with sequelae;
- Fatal;
- Unknown.

10.8. Recording Adverse Events

All AEs occurring during the course of the study must be documented in the Adverse Event page of the eCRF. Moreover, if the Adverse Event is serious, the Serious Adverse Event Form must also be completed.

It is responsibility of the Investigator to collect all adverse events (both serious and non-serious).

The recording period for Adverse Events is the period starting from the beginning of the procedure until the subject’s study participation ends.

Given the significant amount of possible comorbidities in the study population, any condition diagnosed before the start of the procedure will be considered a baseline condition and will be recorded in the Medical History page of the eCRF. The occurrence or worsening of these conditions during and after the study procedure must be recorded as an AE in the eCRF.

The only exception to this rule is represented by congenital anomalies including major organ malformations, genetic diseases and/or chromosomal abnormalities, that should be reported as baseline conditions even if diagnosed after treatment.

If a clinically significant abnormal laboratory finding or other abnormal assessment detected during the study period meets the definition of an AE and is not assessed as pre-existing, then the AE eCRF page must be completed, as appropriate. A diagnosis, if known, or clinical signs and symptoms if diagnosis is unknown, rather than the clinically significant abnormal laboratory finding, should be reported on the AE eCRF page. If no diagnosis is known and clinical signs and symptoms are not present, then the abnormal finding should be recorded as adverse event.

Occurrence of COVID-19 infection during the study will be reported in the Adverse Events section of the eCRF if symptoms judged related to the infection are present. Every effort should be made by the site to confirm all suspected incidences of COVID-19 in accordance with local diagnostic guidelines. Tests for detecting SARS-CoV-2 infection, as well as their results, will be reported in the eCRF. Documentation of testing and results obtained outside the clinical site, should be collected within 14 days of confirmed diagnosis (or whenever possible) and recorded in the eCRF. For all confirmed cases of COVID-19/SARS-CoV-2 the investigator must follow the standard of care in accordance with local treatment guidelines. All concomitant treatments must be recorded in the eCRF as well.

For pharmacovigilance purposes, all SAEs should be followed-up in order to elucidate as completely and practically as possible their nature and/or causality until resolution of all queries, clinical recovery is complete, laboratory results have returned to normal, stable condition is reached or until the subject is lost to follow-up. Follow-up may therefore continue after the subject has left the study. In this case, the follow-up will continue with no timelines for related SAEs, while for unrelated SAEs the type and extent of follow-up undertaken will be determined for each individual case and will depend upon the nature (e.g. events with poor prognosis or which do not resolve), severity and medical significance of the event.

AEs related to the procedure for surfactant administration

The procedure for surfactant administration will last from the application of the laryngoscope up to the removal of the CHF 6440 catheter in the LISA treatment group or the ETT in the comparator arm within one hour after the instillation of poractant alfa.

All AEs during procedures for surfactant administration will be carefully monitored and recorded in both arms. Specific focus will have to be paid on the following AEs:

- Obstruction of the CHF 6440 catheter or ETT;
- Bradycardia;
- Neonatal oxygen desaturation;

- Apnoea;
- Hypotension requiring treatment;
- Any episodes of cough, sneezing, choking, laryngospasm, surfactant reflux, vomiting.

A complete qualitative risk assessment has been conducted to identify and mitigate potential safety risks associated with use of CHF 6440 medical device. The results provide evidence that the benefits of using the device outweigh the residual risks and do not highlight any specific additional risk or safety issue than the ones listed above.

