4.4 Subject Withdrawals

Parents/legal representative have the right to withdraw the subject from the study at any time for any reason.

The Investigator also has the right to withdraw the subjects from the study in the event of:

- An adverse event which is considered intolerable by the Investigator prior to surfactant administration.
- An abnormal laboratory test result that the Investigator considers clinically significant and warranting the withdrawal of the subject prior to surfactant administration.
- A concomitant clinical condition/disorder/anomaly that necessitates pharmacological treatment with a drug which interacts in any way with the study treatment prior to surfactant administration.
- Hypersensitivity to the active substance or to any of the excipients with regards to the second and third possible treatments with proactant alfa (if needed).
- The development of any exclusion criterion prior to surfactant administration.

Detection of COVID-19 infection at the enrollment or during the study does not automatically lead to withdrawal of the subject. It will be up to the investigator's judgement to withdraw

the subject from the study if he/she deems that remaining in the study will place the subject and/or the clinical site at undue risk by continuing their participation. The investigator/site staff must take all necessary precautions to minimize and avoid the risk of transmission and exposure to study subjects and site staff, according to local guidelines.

The Investigator is responsible for the optimal individual treatment for the subject. The Investigator must complete the “Study Termination” page of the electronic case report form (eCRF) explaining the main reason for withdrawal.

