6.2.3.2 Sedation and analgesia

The use of sedative/analgesic medication, as well as the use of atropine, before/during surfactant administration, will be at investigator's discretion and according to each neonatal intensive care unit (NICU) internal standard.

If premedication is used, the Investigator should define a protocol (with specification of drugs and dosages) before starting enrollment, which allows for a step-by-step management of pain and sedation for the endotracheal administration of surfactant. Each neonate will be managed according to the pre-defined protocol, and decision on which step of the protocol to apply should be based on neonate's needs. The same step-by-step protocol should be applied to both treatment arms. The protocol will be provided to the Sponsor.

A first step could be attempted with a non-pharmacological analgesic technique (sucrose, glucose, holding, swaddling and methods of sensorial saturation).

A pharmacological intervention could be given following a progression in the use of sedatives/analgesics, based on neonate's need. As a guidance, examples of pharmacological interventions which can be used (either alone or in combination) are the following:

- Vagolytic agents (e.g. atropine).
- Sedative/analgesics medications with rapid onset and short duration of action (e.g. fentanyl).

The use of sedation/analgesia and other medications will be carefully recorded along with related information (e.g. date and time of administration, dosage and route) in the relevant section of the eCRF.

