7. STUDY PLAN

7.1 Study Schedule

This study will include the following periods and visits:

Periods:

- Pre-randomization period: on admission to the study prior to study treatment;
- Day 1: randomization, before start of study procedure, treatment administration up to end of surfactant administration (T0); up to 24 hours after receiving study treatment (5, 15, 30 min, 1, 6, 12, 24 hours);
- Day 2: from 24 hours to 48 hours post treatment;
- Day 3: from 48 hours to 72 hours post treatment;

- Day 5: from 96 hours to 120 hours post treatment.

Follow-up visits:

- 28 days Post-Natal Age (PNA);
- 36 weeks Post-Menstrual Age (PMA);
- Discharge home or 40 weeks PMA, whichever comes first;
- 24 months (± 3 months) corrected age visit.

Details are reported in the following sections and summarized in the following flowchart ([Table 2](#)):

The following time deviations from theoretical post-dose times will be allowed:

Table 3: ALLOWED TIME DEVIATIONS

Post-dose time assessments	Allowed deviations
5, 15 minutes	+ 1 minute
30 minutes	+ 5 minutes
1 hour	+ 10 minutes
6, 12 and 24 hours	+ 30 minutes
48, 72, and 120 hours	+ 2 hours
28 days PNA	+ 2 days
36 wks PMA	+ 4 days
40 wks PMA (if still in hospital)	+ 2 days
24 months clinical assessment	+ 3 months

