10.9. Reporting Serious Adverse Events to the Sponsor

The Investigator (or delegate) must report all Serious Adverse Events and any UADE to the [REDACTED] Safety Contact listed below within 24 hours of awareness.

Information on SAE (including UADE) must be sent by providing the completed, dated and signed paper Serious Adverse Event form. At a later date, the [REDACTED] Safety Contact will report all information to Chiesi Global Pharmacovigilance, the Clinical Project Manager and the Clinical Research Physician.

Name and Title	Telephone no.	E-mail
██████████ Safety ██████████	Toll free numbers provided separately	████████████████████
████████████████████ Global Pharmacovigilance Chiesi Farmaceutici S.p.A., Parma (Italy)	Phone: ██████████ Fax: ██████████	████████████████████ [contact]

- Reporting of SAEs from the investigator site is from the start of the procedure until the subject's study participation ends. After this date, even if no active monitoring of subjects is required, related SAEs occurring to a subject should be reported if the investigator becomes aware of them.
- Up to the closure of the site, SAEs/UADEs reports should be reported to the ██████████ Safety Contact. New related serious adverse events occurring after the site is closed should be reported directly to the Chiesi Safety Contact.

10.10. Reporting Serious Adverse Events/Unanticipated Adverse Device Effects to Regulatory Authorities/ IRB

The Sponsor or designated CRO will report adverse events to the regulatory authorities in compliance with the timelines and standards of reporting according to local regulations (Guidance for industry and Investigators-Safety Reporting Requirements for INDs and BA/BE studies, December 2012) as well as to the Investigators and Central IRB, if applicable, by MedWatch/CIOMS form. The Investigator (or Sponsor/CRO where required) must inform the IRB per Sponsor instruction upon receipt of the SUSAR notification. An IND and/or NDA Safety Report will be submitted to regulatory authorities unblinded. Participating Investigators and IRB will receive a blinded IND Safety Report, unless otherwise specified.

All UADEs which occur with the medical device will be reported by the sponsor or designated CRO to regulatory authorities, as required, as well as to the Investigators and Central IRB, if applicable, as IND Safety Reports.

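### AE and SAE recording opens at laryngoscope insertion, so harm confined to the interval between open-label randomisation and laryngoscopy is filed as medical history and left out of the safety comparison

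*Protocol*

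**What the plan says.** **When recording opens.** Section 10.8 states: "The recording period for Adverse Events is the period starting from the beginning of the procedure". Section 10.9 uses the same start for serious events: "Reporting of SAEs from the investigator site is from the start of the procedure until the subject's study participation ends".

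**What the start is.** Section 7.1.2 equates the start of the procedure with laryngoscope insertion. Section 10.8 agrees: "The procedure for surfactant administration will last from the application of the laryngoscope up to the removal of the CHF 6440 catheter" (or of the ETT in the control arm).

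**What happens to earlier events.** Under Section 10.8, "any condition diagnosed before the start of the procedure will be considered a baseline condition and will be recorded in the Medical History". That section then adds a limit: if such a condition occurs or worsens during or after the procedure, it must be recorded as an AE.

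**What can happen before the start.** Section 7.1.2 places randomisation first, then a set of pre-procedure assessments, then laryngoscopy. Section 6.2.3.2 leaves to the investigator's discretion the use of sedatives and analgesics, "as well as the use of atropine, before/during surfactant administration". A site that premedicates must define a stepwise protocol before enrolment and use the same one in both arms, but the step is chosen by each neonate's needs. Section 3 describes the trial as open-label.

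**The concern.** After open-label randomisation, differences in care can be a consequence of the assigned arm. Calling the results of that care a baseline condition treats a possible effect of allocation as if it came before allocation. The main objective in Section 2.1 is the comparative safety of two ways of giving surfactant, and some neonates will be premedicated for one or the other with the arm known.

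The events most plausibly affected are ones the protocol itself cares about: Section 10.8 lists bradycardia, desaturation, apnoea and hypotension requiring treatment for specific focus. At stake are the completeness of the safety comparison, possibly unequally by arm, and the sponsor's sight of serious events in randomised neonates.

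**Working it through.** The protocol gives no figure to reproduce here, and no power calculation. The check is a trace of one event through the text, followed by an illustration on stated assumptions.

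**Trace.** Take a neonate who is randomised, receives a sedative, and has an apnoea that resolves before the laryngoscope is placed.

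1. *AE page (10.8):* the event precedes the start of the procedure, so there is no AE record. It goes to Medical History.
2. *SAE report (10.9):* reporting opens at the same moment, so a serious event in this interval has no route to the sponsor.
3. *Procedural safety variables (9):* these count AEs that begin during the overall procedure, so the event is not counted.
4. *Sedation subgroup (12.3.5):* this is limited to AEs during the procedure. It examines sedation with a clock that starts after any pre-laryngoscopy sedation was given.
5. *Vital signs (7.1.2, 12.3.5):* the baseline is the value taken in the 15 minutes before laryngoscopy, which may itself follow premedication.
6. *Populations (12.2):* both the ITT and the Safety population require at least one dose. A neonate withdrawn undosed is in neither.

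If the apnoea recurs or worsens from laryngoscopy onward, Section 10.8 makes it an AE. The loss is therefore confined to harm that begins in the interval and then resolves or persists unchanged.

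**A second cut-off.** Sections 7.1.1 and 7.1.2 send to Medical History whatever is diagnosed before the study drug is given, and Section 7.1.2 speaks of AEs diagnosed after treatment administration. Section 10.8 uses the start of the procedure, which is earlier. A condition arising between laryngoscope insertion and instillation thus has two possible filings.

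**Illustration.** Denominators are from Section 12.1: 100 LISA and 50 conventional (150 × 2/3 and 150 × 1/3). The protocol gives neither the rate of premedication between randomisation and laryngoscopy nor the rate of harm in that interval, so both are assumptions.

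Share of neonates with an unrecorded event = use × harm rate; difference = ETT share − LISA share.

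| Assumed use, LISA / ETT | Assumed harm rate | LISA, of 100 | ETT, of 50 | Difference (points) |
|---|---|---|---|---|
| 50% / 50% | 5% to 20% | 2.5 to 10 (2.5% to 10%) | 1.25 to 5 (2.5% to 10%) | 0 |
| 40% / 50% | 10% | 4 (4%) | 2.5 (5%) | 1 |
| 30% / 80% | 5% to 20% | 1.5 to 6 (1.5% to 6%) | 2 to 8 (4% to 16%) | 2.5 to 10 |
| 80% / 30% | 5% to 20% | 4 to 16 (4% to 16%) | 0.75 to 3 (1.5% to 6%) | −2.5 to −10 |

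For any endpoint that counts neonates with at least one AE, these are maxima for each scenario. A neonate who also has a counted AE is already in the numerator, so overlap shrinks the shift. The difference is also zero if the products of use and harm are equal, or if no harm precedes laryngoscopy.

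**The case against.** **The start was chosen deliberately.** The version history records the move from consent to the start of the procedure in version 4.0, and Section 10.8 gives the heavy comorbidity of this population as the reason for its baseline rule. Section 2.1 names events during the overall procedure, Section 10.4 describes the procedure without premedication, and Section 5.1 treats premedication as concomitant medication. This stands as a reason not to return to consent, and to leave the procedural window alone. It does not justify calling post-randomisation events baseline, because a start at randomisation also keeps earlier comorbidity out.

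**Most premedication harm is still captured.** A reader might infer that all harm from premedication drops out. It does not: occurrence or worsening during or after the procedure is an AE, and recording then runs to the end of participation.

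**The arms share a premedication protocol.** A reader might also infer that the bias is known to be differential, or to favour one arm. The documents do not support that. The common site protocol reduces imbalance. It does not rule imbalance out, because the step is chosen per neonate with the arm known.

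**Section 4.4 does not prove a contradiction.** It allows withdrawal for "An adverse event which is considered intolerable by the Investigator prior to surfactant administration". That phrase also covers laryngoscopy and failed attempts, which lie inside the AE window, so it can be read consistently with Section 10.8. The main reason for withdrawal goes on the Study Termination page. What remains is that an event before laryngoscopy leading to such a withdrawal would have no AE record.

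**Serious events are not wholly unreported.** Section 10.11 has investigators report adverse reactions to marketed concomitant medicines to the Health Authority. That is a partial safeguard, and it provides no route to the sponsor.

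**Conclusion.** The gap is real on the text and narrow in scope. Harm that begins after randomisation and before laryngoscopy, and does not recur or worsen afterwards, is filed as Medical History. It is absent from the AE comparison and the sedation subgroup, and it has no SAE route to the sponsor. The filing rule applies whatever the cause; premedication is the most evident exposure in the interval.

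The loss may differ between arms, but neither its size nor its direction can be derived from the protocol. The illustrated range of 0 to 10 points either way rests wholly on assumed use and harm rates, and on premedication being given after randomisation, a sequence the protocol does not fix. With equal use and equal harm the comparison is not shifted, but the SAE reporting gap remains. The trace can be stated with high confidence; a claim of actual bias cannot. The conflicting Medical History cut-offs need reconciling in any case.

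**What to change.** - **Sections 10.8 and 10.9:** start AE recording and SAE reporting at randomisation in both arms. Restrict Medical History to conditions present before randomisation, and keep the existing exception for congenital anomalies diagnosed later.
- **Sections 7.1.1 and 7.1.2:** replace the cut-off tied to drug administration so that these sections agree with Section 10.8.
- **Procedural endpoints:** keep the window from laryngoscope insertion to removal of the catheter or ETT.
- **Reporting:** show events from randomisation to laryngoscopy as a separate line by randomised arm, for all randomised neonates. Say explicitly that this includes those withdrawn undosed, since Section 12.2 would otherwise exclude them.
- **Avoid** opening the window at the first premedication dose. Observation time would then depend on an unblinded, discretionary choice, and background apnoea or desaturation would be counted for longer in the arm premedicated more.

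The cost is a protocol wording change and a few more AE records. The supporting data are largely in place: Section 6.2.3.2 already records the date and time of sedation and analgesia, and Section 6.2.3.1 already requires cardiorespiratory monitoring before the procedure. No clinical management changes.
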